#### 9.5.4.1 Laboratory Safety Evaluations (Hematology, Chemistry, Coagulation, and Urinalysis)

Laboratory tests for hematology, chemistry, coagulation, and urinalysis are specified in Appendix 2.

#### 9.5.4.2 Pregnancy Test

All women who are being considered for participation in the study, and who are not surgically sterilized or postmenopausal (as defined in Appendix 5), must be tested for pregnancy within 72 hours of first dose of study treatment. If a urine test is positive or not evaluable, a serum test will be required. Participants must be excluded/discontinued from the study in the event of a positive test result. Repeated Pregnancy test (such as monthly test) may be conducted if required by local regulations.

[figure not shown]
#### 9.5.4.3 Hepatitis B and C Serology

[figure not shown]
Serology for Hepatitis B and Hepatitis C will be performed for all participants. Required tests are indicated in Table 21 in Appendix 2.

[figure not shown]
#### 9.5.5 Performance Assessments

##### 9.5.5.1 Eastern Cooperative Oncology Group Performance Scale

The investigator or qualified designee will assess ECOG PS (see Appendix 6) at screening (within 7 days of randomization), prior to the administration of each dose of study treatment, and during the Post-treatment Follow-up Phase as specified in Section 2 - SoA. ECOG PS must be 0 or 1 on the first day of dosing.

## **9.9 Visit Requirements**

Visit requirements are outlined in Section 2 – Schedule of Activities (SoA). Specific procedure-related details are provided above in Section 9 – Study Assessments and Procedures.

### **9.9.1 Screening**

Approximately 28 days prior to treatment randomization, potential participants will be evaluated to determine that they fulfill the entry requirements as set forth in Sections 6.1 and 6.2. Screening procedures may be repeated after consultation with MSD.

Written consent must be obtained prior to performing any protocol-specific procedure. Results of a test performed prior to the participant signing consent as part of routine clinical management are acceptable in lieu of a screening test if performed within the specified time frame. Screening procedures are to be completed within approximately 28 days prior to the first dose of study treatment except for the following:

- Laboratory tests are to be performed within 10 days prior to the first dose of study treatment. An exception is hepatitis testing which may be done up to 40 days prior to randomization if done as part of standard documented clinical activities. Screening labs should be collected and assessed prior to randomizing the participant.
- Evaluation of ECOG PS is to be performed within 7 days prior to date of randomization.
- For women of reproductive potential, a urine or serum pregnancy test will be performed within 72 hours prior to the first dose of study treatment. If urine pregnancy results cannot be confirmed as negative, a serum pregnancy test will be required (performed by the local study site laboratory).
- Tumor tissue sample collection is not required to be obtained within 28 days prior to the first dose of study treatment. Tumor specimen must be received by the central vendor before a participant is randomized.

Participants may be rescreened after initially failing to meet the inclusion/exclusion criteria. Results from assessments during the initial screening period are acceptable in lieu of a repeat screening test if performed within the specified time frame and the corresponding inclusion/exclusion criteria are met. Participants who are rescreened will retain their original screening number.

### 9.9.2 Treatment Phase

Visit requirements are outlined in Section 2 - SoA. Specific procedure-related details are provided in Section 9.1. At Cycle 1 Day 1, results from Screening Visit evaluations should be reviewed to determine whether the participant continues to meet the eligibility requirements, as specified in Section 6.

Treatment with pembrolizumab will occur every 21 days (1 cycle) for up to 35 cycles (approximately 2 years). The maximum duration of the initial Treatment Phase is specified as 35 cycles of treatment (approximately 2 years) unless a discontinuation criterion is met (Section 8.1).

Epacadostat will be dosed BID during the Treatment Phase. Treatment may continue until Cycle 35 Day 21, unless a discontinuation criterion is met (Section 8.1).

The EXTREME regimen treatments will occur every 21 days (1 cycle) for up to 6 cycles for 5-FU and cisplatin/carboplatin. Cetuximab will be administered weekly until radiographic PD or unacceptable toxicity.

### 9.9.3 End of Treatment

When the participant permanently discontinues study treatments, the EOT Visit should be conducted. If the EOT Visit coincides with a regular study visit, the EOT evaluations will supersede those of that scheduled visit. The participant should be encouraged to return for the Post-treatment Safety Follow-up Visit.

### 9.9.4 Post-treatment Visits

#### 9.9.4.1 Safety Follow-up Visit

**NOTE: As of Amendment 04, the Safety Follow-up Visit will be the last visit in the study. This section has been amended accordingly.**

The mandatory Safety Follow-up Visit should be conducted approximately 30 days after the last dose of study treatment or before the initiation of a new anticancer treatment, whichever comes first.

A participant will be considered to have completed this study once they have attended this visit. Participants currently in Follow-up or in Survival Follow-up are considered to have completed the study; these participants are not required to attend any further visits. Assessment and recording of AEs will be performed as per Section 9.3.

Participants who are eligible to enter Second Course retreatment with pembrolizumab plus epacadostat or pembrolizumab monotherapy may have up to 2 Safety Follow-up Visits; 1 after the initial treatment period and 1 after the Second Course study treatment.

#### 9.9.4.2 Follow-up Visits

**NOTE: As of Amendment 04, this section is no longer applicable. Participants currently in post-treatment follow-up are considered to have completed the study once they have attended the Safety Follow-up Visit; assessment and recording of AEs will be performed as per Section 9.3.**

Participants who discontinue study treatment for a reason other than BICR-verified radiographic disease progression will move into the Post-treatment Follow-up Phase and should be assessed by radiologic imaging every 6 weeks (42 days  $\pm$  7 days) for the first year and every 9 weeks (63 days  $\pm$  7 days) thereafter to monitor disease status. Every effort should be made to collect imaging until BICR-verified radiographic disease progression, the start of a new anticancer therapy, withdrawal of consent for imaging, pregnancy, death, or the end of the study. Information regarding post-study anticancer treatment will be collected if new treatment is initiated.

Participants who are eligible to receive retreatment with pembrolizumab plus epacadostat or pembrolizumab monotherapy according to the criteria in Section 7.2.6 will move from the Post-treatment Follow-up Phase to the Second Course Phase when they experience disease progression.

#### 9.9.4.3 Survival Follow-up

**NOTE: As of Amendment 04, this section is no longer applicable. Participants currently in survival follow-up are considered to have completed the study; these participants will no longer be contacted for survival information. Assessment and recording of AEs will continue as per Section 9.3.**

Participants who experience BICR-verified PD or start a new anticancer therapy, whichever comes first, will move into the Survival Follow-up Phase and should be contacted by telephone approximately every 12 weeks starting from the last point of contact to assess for survival status along with new anticancer therapy until death, withdrawal of consent, lost to follow up or the end of the study, whichever occurs first.

#### 9.9.5 Second Course Phase

Second Course Phase is described in Section 7.2.6. Visit requirements are outlined in Section 2.2 - SoA. Specific procedure-related details are provided in Section 9.1.

#### 9.9.6 Unscheduled Visits

Unscheduled visits may occur at any time at the investigator's discretion or if medically warranted. Appropriate clinical and laboratory measurements may be performed based on AEs or other findings. The visit, and any assessments, must be recorded in eCRF.

#### 9.9.7 Survival Status

**NOTE: As of Amendment 04, this section is no longer applicable; survival data is no longer being collected.**

To ensure current and complete survival data is available at the time of database locks, updated survival status may be requested during the course of the study by MSD. For example, updated survival status may be requested prior to but not limited to an external Data Monitoring Committee (eDMC) review, interim and/or final analysis. Upon MSD notification, all participants who do not/will not have a scheduled study visit or study contact during MSD defined time period will be contacted for their survival status (excluding participants that have a previously recorded death event in the collection tool).

### 10. Statistical Analysis Plan

This section outlines the statistical analysis strategy and procedures for the study. If, after the study has begun, changes are made to primary and/or key secondary hypotheses, or the statistical methods related to those hypotheses, then the protocol will be amended (consistent with ICH Guideline E-9).

## 10.1 Statistical Analysis Plan Summary

Key elements of the statistical analysis plan are summarized below; the comprehensive plan is provided in Sections 10.2 through 10.12.

Study Design Overview	A Phase 3 Randomized, Open-Label Clinical Study to Evaluate the Efficacy and Safety of Pembrolizumab plus Epacadostat, Pembrolizumab monotherapy and the EXTREME Regimen as First line Treatment for Recurrent or Metastatic Head and Neck Squamous Cell Carcinoma (KEYNOTE-669)
Treatment Assignment	Approximately 90 participants will be randomized 2:1:2 into 3 treatment arms, stratified by ECOG PS, HPV p16 status and prior systemic therapy (see Section 7.3.1 for details). The treatment arms are as follows: 
 
• pembrolizumab 200 mg Q3W + epacadostat;
 
• pembrolizumab 200 mg Q3W
 
• cetuximab + platinum + 5-FU (EXTREME)
 
 This study will be conducted as an open-label study.
Analysis Populations	Efficacy: Intention to Treat (ITT) Safety: All Participants as Treated (APaT)
Primary Endpoint(s)	Objective Response Rate (ORR) per RECIST 1.1 assessed by investigator determination
Statistical Methods for Key Efficacy Analyses	ORR will be estimated by treatment group with 95% CI calculated by Clopper and Pearson exact method [Clopper, C. J. and Pearson, E. S. 1934].
Statistical Methods for Key Safety Analyses	Point estimates (count and percentage) by treatment group will be provided for safety endpoints.
Interim Analyses	Efficacy 
 
• Final analysis
 
 Timing: When all randomized participants have one post-baseline imaging scan or discontinue the study. Safety: One safety review will be conducted at ~ 4 month after first participant is randomized.
Multiplicity	There will be no multiplicity adjustment.
Sample Size and Power	The sample size is approximately 90 participants with 36 participants in each of the pembrolizumab + epacadostat and EXTREME arms, and 18 participants in the pembrolizumab monotherapy arm. Section 10.9 provides the precision of the ORR estimates.

## 10.2 Responsibility for Analyses/In-House Blinding

The statistical analysis of the data obtained from this study will be the responsibility of the MSD Clinical Biostatistics department.

MSD will generate the randomized allocation schedule(s) for study treatment assignment for this protocol, and the randomization will be implemented in IVRS.

Although the study is open-label, analyses or summaries generated by randomized treatment assignment and actual treatment received will be limited and documented.

The eDMC will serve as the primary reviewer of the unblinded safety data. Additional logistical details will be provided in the eDMC Charter.

### **10.3 Hypotheses/Estimation**

Objectives of the study are stated in Section 4.0.

### **10.4 Analysis Endpoints**

#### **10.4.1 Efficacy Endpoint**

##### **Objective Response Rate (ORR) – RECIST 1.1 by investigator determination**

Objective response rate (ORR) is defined as the proportion of the participants in the analysis population who have a best response of complete response (CR) or partial response (PR). Responses are based on RECIST 1.1 by investigator determination.

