## 5. Study Design

### 5.1 Overall Design

**Note: Enrollment was stopped strategically on 02-MAY-2018. 89 participants were randomized in the study. As of Amendment 04, all study efficacy procedures will discontinue after first on-study imaging at Week 9 ( $\pm$  7 days); thereafter participants will be treated as per SoC for the disease and local guidelines. Safety procedures will continue as per protocol for all participants in Group 1 and 2 continuing study treatment. For Group 3 participants continuing study treatment after first on-study imaging at Week 9 ( $\pm$  7 days), safety procedures will continue as per SoC. The last study visit is the Safety Follow-up Visit. This section has been updated accordingly.**

This is a randomized, active-controlled, 3 parallel-groups, multi-site, open-label Phase 3 study evaluating pembrolizumab plus epacadostat, pembrolizumab monotherapy, and the EXTREME regimen in participants with R/M HNSCC who have not received prior systemic therapy for R/M disease. The EXTREME arm was selected as a comparator since it is the SoC per NCCN guideline, while the pembrolizumab monotherapy arm was included to identify the contribution of the individual components of the pembrolizumab plus epacadostat arm. The study has a primary endpoint of ORR. The study will be conducted in conformance with Good Clinical Practices (GCP).

The study includes a Screening period, a Treatment period, and a Post-treatment Safety Follow-up period. After signing the informed consent, candidate participants will be screened against all the eligibility criteria. Eligible participants will be centrally randomized in a 2:1:2 ratio and will be stratified based on:

- ECOG PS (0 vs. 1)
- HPV p16 expression status (either oropharynx-p16 positive vs. oropharynx-p16 negative or larynx/hypopharynx/oral cavity HNSCC); and
- Prior systemic oncological therapy (as part of the definitive treatment for locally advanced disease) (yes vs. no).

Originally, approximately 625 eligible participants with R/M HNSCC who meet the inclusion/exclusion criteria were to be enrolled in the study and centrally randomized in a 2:1:2 ratio in 3 treatment groups:

- Group 1: Pembrolizumab 200 mg 30-minute IV infusion Q3W  $\leq 35$  cycles plus epacadostat 100 mg PO BID  $\leq 35$  cycles
- Group 2: Pembrolizumab 200 mg 30-minute IV infusion Q3W  $\leq 35$  cycles
- Group 3: EXTREME regimen:

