#### 5.4.1.1.2 Modified RECIST for Immune-based Therapeutics (iRECIST)

**NOTE: As of Amendment 04, this section is no longer applicable; iRECIST data will no longer be collected. Participants with radiographic disease progression as determined by RECIST 1.1 will discontinue from the study and followed for safety monitoring, as detailed in Section 9.3; no confirmatory scans are required.**

RECIST 1.1 will be adapted to account for the unique tumor response characteristics seen following treatment with immunotherapeutic agents. Immunotherapeutic agents such as pembrolizumab may produce antitumor effects by potentiating endogenous cancer-specific immune responses. The response patterns seen with such an approach may extend beyond the typical time course of responses seen with cytotoxic agents, and participants treated with pembrolizumab may manifest a clinical response after an initial increase in tumor burden or even the appearance of new lesions.

Thus, standard RECIST 1.1 may not provide an accurate response assessment of immunotherapeutic agents such as pembrolizumab. Based on an analysis of participants with melanoma enrolled in KEYNOTE-001, 7% of evaluable participants experienced delayed or early tumor pseudo-progression. Of note, participants who had PD by RECIST 1.1 but not by the immune-related response criteria [Wolchok, J. D., et al 2009] had longer OS than participants with PD by both criteria [Hodi, F. S., et al 2014]. Additionally, the data suggest that RECIST 1.1 may underestimate the benefit of pembrolizumab in approximately 15% of participants [Hodi, F. S., et al 2016]. These findings support the need to apply a modification to RECIST 1.1 that takes into account the unique pattern of atypical responses in

immunotherapy and enables treatment beyond initial radiographic progression, if the participant is clinically stable.

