#### 9.2.1.1 Initial Tumor Imaging

**Note: As of Amendment 04, central review of imaging is no longer applicable. This section has been updated accordingly.**

Initial tumor imaging at screening must be performed within -28 to -1 days prior to the date of randomization. The site study team must review screening images to confirm the participant has measurable disease per RECIST 1.1.

Tumor imaging performed as part of routine clinical management is acceptable for use as screening tumor imaging if it is of diagnostic quality and performed within -28 to -1 days prior to the date of randomization and can be assessed by the central imaging vendor.

If brain imaging is performed to document the stability of existing metastases, MRI should be used if possible. If MRI is medically contraindicated, CT with contrast is an acceptable alternative.

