### 9.2.1.3 End of Treatment and Follow-up Tumor Imaging

**Note: As per Amendment 04, there is no protocol specified imaging after the Week 9 assessment. This section has been updated accordingly.**

For participants who discontinue study treatment before the Week 9 imaging assessment for efficacy analysis, tumor imaging should be performed at the time of treatment discontinuation ( $\pm$ 4 week window). If previous imaging was obtained within 4 weeks prior to the date of discontinuation, then imaging at treatment discontinuation is not mandatory. For participants who discontinue study treatment due to radiographic disease progression, this is the final required tumor imaging.

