### 9.2.1.6 iRECIST Assessment of Disease (Group 1 and 2)

**NOTE: As of Amendment 04, this section is no longer applicable; iRECIST data will no longer be collected. Participants with radiographic disease progression as determined by RECIST 1.1 will discontinue from the study and be followed for safety monitoring, as detailed in Section 9.3; no confirmatory scans are required.**

iRECIST is based on RECIST 1.1, but adapted to account for the unique tumor response seen with immunotherapeutic agents and therefore is only required for participants in Group 1 and Group 2. iRECIST will be used by the investigator to assess tumor response and progression, and make treatment decisions. When clinically stable, Group 1 and 2 participants should not be discontinued until progression is confirmed by the investigator, working with local radiology, according to the rules outlined in Appendix 8. This allowance to continue treatment despite initial radiologic PD takes into account the observation that some participants can have a transient tumor flare in the first few months after the start of immunotherapy, and then experience subsequent disease response. These data will be captured in the clinical database.

Clinical stability is defined as the following:

- Absence of symptoms and signs indicating clinically significant progression of disease
- No decline in ECOG PS
- No requirements for intensified management, including increased analgesia, radiation, or other palliative care.

Any participant deemed **clinically unstable** should be discontinued from study treatment at central verification of site-assessed first radiologic evidence of PD and is not required to have repeat tumor imaging for confirmation of PD by iRECIST.

If the investigator decides to continue treatment, the participant may continue to receive study treatment and the tumor assessment should be repeated 4 to 8 weeks later to confirm PD by iRECIST, per investigator assessment. Images should continue to be sent in to the central imaging vendor for potential retrospective BICR.

If repeat imaging does not confirm PD per iRECIST, as assessed by the investigator, and the participant continues to be clinically stable, study treatment may continue and follow the regular imaging schedule. If PD is confirmed, participants will be discontinued from study treatment.

[figure not shown]

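### Does the ORR definition in Section 10.4.1 need to say which scans feed best response, and how a participant with no post-baseline scan is counted?

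*Combined protocol and SAP*

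**What the plan says.** ORR is defined in the same way in Section 1 (Synopsis), Section 4 and Section 10.4.1: "the proportion of the participants in the analysis population who have a best response of complete response (CR) or partial response (PR", by investigator assessment under RECIST 1.1. Section 10.5.1 takes all randomised participants as the efficacy population. Section 10.6.1 asks for a by-arm estimate with a Clopper-Pearson 95% CI, and Section 10.8 states that nothing is tested.

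The imaging rules after Amendment 04 are these:

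- Section 5.1: "all study efficacy procedures will discontinue after first on-study imaging at Week 9".
- Section 9.2.1.2: results of later standard-of-care scans are not collected, only their dates.
- Section 9.2.1.3: a participant who stops treatment before Week 9 has a scan at discontinuation, with one waiver: "If previous imaging was obtained within 4 weeks prior to the date of discontinuation, then imaging at treatment discontinuation is not mandatory".
- Section 10.1: the final analysis takes place once every randomised participant has had one post-baseline scan or has left the study.

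**The concern.** Best response is a maximum over a set of assessments, and the set is not named. The Amendment 04 notes stop future collection after Week 9, but they do not say what happens to results already in the database. Some participants were well past Week 9 by then, since Section 9.9.4.1 says: "Participants currently in Follow-up or in Survival Follow-up are considered to have completed the study". Retired text shows that repeated imaging had been planned, both on treatment (Section 9.2.1.6: "study treatment may continue and follow the regular imaging schedule") and afterwards (Section 9.9.4.2: participants "should be assessed by radiologic imaging every 6 weeks"). The sole primary result could therefore be a first-scan response rate, or a best response over unequal follow-up, and a reader might not know which. Section 5.4.1.1.2 says of immunotherapy that "The response patterns seen with such an approach may extend beyond the typical time course of responses seen with cytotoxic agents", which raises the possibility that the choice would matter more in Groups 1 and 2 than in Group 3.

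The second worry is the participant with no post-baseline scan. Section 9.2.1.1 states: "Initial tumor imaging at screening must be performed within -28 to -1 days prior to the date of randomization". The waiver in Section 9.2.1.3 does not exclude that screening scan. Read literally, a participant screened on day -1 who stops by day 27 (-1 + 28) need not be scanned again. If such participants were dropped from the denominator, the ORR would rise.

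**Working it through.** **Reproducing the plan's figures.** Section 10.9 plans 90 participants at 2:1:2: 90 × 2/5 = 36, 90 × 1/5 = 18 and 90 × 2/5 = 36. The Clopper-Pearson limits for x responders among n are the 2.5% quantile of Beta(x, n − x + 1) and the 97.5% quantile of Beta(x + 1, n − x). Nine of the ten rows in Tables 19 and 20 reproduce exactly. For 11/36 the lower limit is 16.3 against a printed 16.4, a last-digit difference. The denominators are the full 36 and 18.

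**No-scan participants.** The numerator in Section 10.4.1 is those who have a CR or PR. The denominator in Section 10.5.1 is everyone randomised. A participant without a post-baseline scan is in the second and not in the first, and so is a non-responder. Excluding them would change the estimate, but Section 10.5.1 does not allow it. For scale, with numbers of unscanned participants assumed because the documents give none:

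| Responders | Everyone randomised | Unscanned excluded (not allowed) |
|---|---|---|
| 14 of 36 | 38.9% (23.1, 56.5) | 6 excluded: 14/30 = 46.7% (28.3, 65.7) |
| 5 of 18 | 27.8% (9.7, 53.5) | 3 excluded: 5/15 = 33.3% (11.8, 61.6) |

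The waiver therefore has no effect on how anyone is classified. A participant who uses it is a non-responder, as is one who dies or withdraws before Week 9.

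**Which scans count.** With one post-baseline scan, best response equals first response. The two readings differ only for a participant who had no CR or PR at the first scan, was scanned again under the old schedule, had that RECIST result recorded before Amendment 04, and showed a CR or PR on it. Survival Follow-up is an unlikely source of such cases, because Section 9.9.4.3 shows that it was entered on verified progression or new anticancer therapy. The documents give no scan counts, no first randomisation date and no on-treatment imaging interval from before the amendment, so the number cannot be estimated and may be zero.

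Per participant, the shift is 1/36 = 2.8 points or 1/18 = 5.6 points. With assumed numbers of late responders:

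| First scan only | Late responders added | ORR (95% CI) |
|---|---|---|
| 11/36 = 30.6% (16.3, 48.1) | 1 | 33.3% (18.6, 51.0) |
| | 2 | 36.1% (20.8, 53.8) |
| | 4 | 41.7% (25.5, 59.2) |
| 5/18 = 27.8% (9.7, 53.5) | 1 | 33.3% (13.3, 59.0) |
| | 2 | 38.9% (17.3, 64.3) |

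Every shifted estimate lies inside the interval it started from. Across the two tables the half-width runs from (48.1 − 16.3)/2 = 15.9 points for 11/36 to (74.0 − 26.0)/2 = 24.0 points for 9/18.

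**The case for a change.** The strongest argument for acting is that this is an open-label study with investigator-read response and a single efficacy endpoint. A choice between two scan sets is best written down before ORR is tabulated by arm, and it would cost a sentence or two. The trigger in Section 10.1 sets when the analysis is done. It is not a cut-off for each participant, and an early participant could have several results on file when the last one reaches a first scan.

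What stands is that no current passage says whether results obtained after Week 9 and held before the amendment enter best response. The rest is weaker. A late choice does harm when it can move a test, a contrast or a decision threshold, and this plan has none of these. Section 10.2 also requires by-arm summaries to be limited and documented. The Amendment 04 passages all lean towards a first-scan response and do not conflict with one another. The suggestion that Groups 1 and 2 would be affected more rests on background text in a section marked no longer applicable, and no late response rates by arm are given to support it.

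**Conclusion.** No change follows. The no-scan question is answered by Sections 10.4.1 and 10.5.1 read together, and Tables 19 and 20 are built on the same full denominators. The scan-set question is a real but small omission. It affects only results collected before Amendment 04, which the documents do not show to exist. Its size is unknown and possibly zero, at 2.8 or 5.6 points per participant classified differently, well inside intervals whose half-widths are about 16 to 24 points. Either reading gives a valid by-arm estimate in a study reduced to preliminary estimation, and no between-arm bias is shown. The analyst will have to choose a scan set to program the endpoint, and a table footnote tells the reader which was used.

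This rests on two assumptions: that the intention-to-treat population is applied as written, and that no formal comparison is added later. If a between-arm test or a decision rule were introduced, the scan set would need to be fixed beforehand.
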